## **List of Abbreviations:**

BIS: bispectral index

CO: cardiac output

CONSORT: Consolidated Standards of Reporting Trials

ERAS: Enhanced Recovery After Surgery

EEG: electroencephalography

FiO2: fraction of inspired oxygen

GDT: goal-directed therapy

OLV: one-lung ventilation

PaO2: arterial partial pressure of oxygen

## 1. Introduction

Patients undergoing thoracotomy in thoracic surgery are prone to have complications of delayed recovery from general anesthesia and perioperative instable hemodynamics due to the relatively invasive procedures and patient's underlying morbidity. Therefore, intraoperative monitoring and corresponding management are of great importance to prevent relevant complications in thoracic surgery. This study aims to investigate the clinical benefits of two intraoperative monitoring techniques in patients undergoing thoracotomy surgery, including depth of anesthesia and minimally invasive cardiac output monitoring. First, M-Entropy system will be used to measure the depth of anesthesia and be evaluated regarding the effect of spectral entropy guidance on postoperative recovery. Second, we will apply ProAQT device in guiding goal-directed hemodynamic therapy and assess its impact on occurrence of postoperative pulmonary complications and recovery. In this study, we will conduct a factorial parallel randomized controlled trial and use the method of stratified randomization to evaluate both two monitoring technologies in the same patient group. The results of this study will provide important evidence and clinical implication for precision anesthesia and enhanced recovery after surgery (ERAS) protocol in thoracic surgery.

This study aims to investigate the clinical benefits of two intraoperative monitoring techniques in patients undergoing thoracotomy surgery, including M-Entropy system and ProAQT sensor, as follows:

- 1) To evaluate the effect of M-Entropy guidance on the emergence from anesthesia and risk of postoperative delirium.
- 2) To apply ProAQT in guiding goal-directed hemodynamic therapy and assess its impact on postoperative pulmonary complications and recovery.

## 2. Background

Thoracic anesthesia comprises a wide variety of diagnostic and therapeutic procedures involving the lungs, airways, and hemodynamic changes. The procedure of thoracotomy inevitably causes pneumothorax, which results in multiple physiology derangements, including ventilation-perfusion mismatch and hypoxia. Furthermore, one-lung ventilation (OLV) is commonly used to facilitate the visualization and surgical manipulation in video-assisted thoracotomy. However, OLV may also cause profound hemodynamic changes, including lung collapse, barotrauma and severe hypotension. The hemodynamic instability may further increase the risk of inadequate depth of anesthesia and thereafter its related complications, such as intraoperative awareness, post-traumatic stress disorder and cognitive dysfunction. Therefore, intraoperative monitoring and corresponding management are of great importance to prevent relevant complications in thoracic surgery.

Because of the advances in monitoring technology in recent decades, the risk of mortality and morbidity of anesthetic practices has significantly declined. Among the newly-introduced technologies, electroencephalography (EEG)-based monitoring of anesthesia depth and indirect cardiac output monitoring are useful and minimally invasive in optimizing the anesthetic patients' intraoperative hypnotic, cardiac output, and intravascular volume status. However, there is sparse evidence regarding the effectiveness of the use of these two monitoring in guiding thoracic anesthesia. Accordingly, this study aims to investigate the effect of guidance of spectral

entropy and indirect cardiac output monitoring on the recovery from anesthesia and postoperative outcomes in patients undergoing thoracotomy.

### ***Anesthesia depth monitoring using spectral entropy***

Meta-analysis has showed that bispectral index (BIS)-guided anesthesia may enhance early recovery time in patients undergoing surgery with general anesthesia compared to clinical signs. However, compared with BIS, M-Entropy™ system (GE Healthcare, Helsinki, Finland) is much less investigated regarding its clinical effectiveness. The use of entropy to track the anesthetic state of patients is a relatively new monitoring approach. Entropy measures the degree of disorder or the lack of synchrony or consistency in a system. Entropy-based analyses have been applied to the EEG and used to construct EEG-based indices meant to indicate the depth of anesthesia. Although EEG-based monitoring of anesthesia depth is widely used and effective in maintaining the optimal range of anesthesia depth in total intravenous anesthesia, there is sparse evidence regarding the role of spectral entropy monitoring in volatile anesthesia regarding time to emergence from anesthesia as well as reduction in anesthetic agent use. Besides, whether entropy guidance in general anesthesia protects against development of postoperative delirium remains unclear in thoracic surgery.

### ***Indirect cardiac output monitoring in guiding intraoperative fluid and inotrope or vasopressor therapy***

There are several commercial devices in monitoring cardiac output (CO) through minimal invasive techniques. The major principles and techniques of CO measurement include the Fick principle, arterial waveform analysis techniques, the Doppler principle. ProAQT® device (Pulsion Medical Systems, Munich, Germany) is a modular platform with intelligent visualization for real-time patient monitoring on the basis of PiCCO pulse contour algorithm. ProAQT allows physiological interpretation of the patient's hemodynamic status and supports goal directed therapy in surgical patients. Regardless of the broad use of minimally invasive CO monitoring in clinical practices, the evidence for its benefits in patients' prognosis is conflicting. Furthermore, it is unclear whether application of minimally invasive CO monitoring in guiding administration of intraoperative fluid, inotrope, and vasopressor improves outcomes in thoracic surgery. At present, the validity of this technology as a valid guide for fluid management when the chest is open remains unclear. Strong clinical outcomes data support the use of noninvasive stroke volume monitors in patients undergoing major surgery although these studies generally do not focus on thoracic surgical procedures.

### ***The value of precision anesthesia in Enhanced Recovery After Surgery (ERAS)***

Patients undergoing thoracotomy are prone to have complications of delayed recovery from general anesthesia and perioperative instable hemodynamics due to the relatively invasive procedures and patient's underlying morbidity. Current recommendations from the ERAS Society and the European Society of Thoracic Surgeons include short-acting anesthetics to facilitate early emergence, opioid-sparing analgesia, euvolemic fluid management, etc. In achieving early emergence from general anesthesia and euvolemic status during surgery, we could add important evidence and provide useful clinical implication to ERAS protocols by elucidating the effectiveness of precision guidance of anesthesia depth and goal-directed

hemodynamic therapy using real-time spectral entropy and minimally invasive CO monitoring in thoracic anesthesia.

### 3. Criteria of Eligibility

We will enroll the patients undergoing video-assisted thoracotomy at Shuang Ho Hospital, Taipei Medical University, New Taipei City, Taiwan. Exclusion criteria will be age < 20 years, pregnancy, end-stage renal disease, emergency surgery, presence of circulatory shock needing vasoactive drugs before surgery, any diagnosis of aortic diseases, cerebral vascular diseases or trauma, and high-degree cardiac arrhythmia (e.g. atrial fibrillation), uses of cardiac pacemaker or automated implantable cardioverter defibrillator, New York Heart Association functional classification 4, long-term use of psychiatric medications, intraoperative blood loss > 1 L, intraoperative blood transfusion, planned or unanticipated transfer to intensive care unit for postoperative mechanical ventilation, and patient refusal to participate.

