### 4. Study Design

We will use the design of factorial parallel randomized controlled trial to conduct these two studies in the same patient group. A computer-generated list of randomizations (Research Randomizer, [www.randomizer.org](http://www.randomizer.org)) will be used for these group allocations. We will use stratified randomization method to ensure random allocations of these two treatments (spectral entropy and ProAQT goal-directed therapy) in all patients. Allocation will be concealed with sequentially numbered sealed opaque envelopes. The principal investigator will open the respective concealed envelope containing the patient allocation to the treatment arm on the day of surgery immediately before induction of anesthesia. In this trial, we will conform to the recommendations in the Consolidated Standards of Reporting Trials (CONSORT) statement. In addition, we will follow the principle of intention-to-treat in our analyses of the trial results.

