In the M-Entropy group, dosage of volatile anesthetics will be adjusted to achieve the response and state entropy values between 40 and 60 from the start of anesthesia to the end of surgery. In the control group, dosage of volatile anesthetics will be titrated according to clinical judgment. This will be to maintain mean arterial pressure and heart rate within 20% range of the baseline. In case of signs of inadequate anesthesia (e.g. movement, cough and swallowing), anesthetic dose will be increased. M-Entropy monitoring will be continued in the control group, but the entropy number and EEG waveform will be concealed from the anesthetist in charge. Entropy values, hemodynamic, and expiratory gas data will be recorded in 5-min intervals. In all patients, cessation of general anesthesia will be timed to facilitate early awakening after wound closure. After reversal of the neuromuscular blocking agent and response to verbal command, all subjects will be extubated at the operating room and then transferred to the postanesthetic care unit. In the postoperative period, surgeons, medical and nursing staff at the postanesthetic care unit will be blinded to group allocation.

Primary outcome is time to spontaneous eye opening. Secondary outcomes include time to tracheal extubation, time to orientation in time and place, time to leave operating room, and events of emergence agitation, postoperative delirium, and intraoperative recall or awareness. We will use the Richmond Agitation-Sedation Scale to evaluate the level of agitation and sedation promptly after extubation. Events of delirium will be evaluated using the Confusion Assessment Method at the postanesthetic care unit 30 minutes after tracheal extubation. An independent adjudicator blinded to the group allocation will measure all the outcomes.

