### **The effect of application of ProAQT in guiding goal-directed hemodynamic therapy on postoperative recovery: A single-blind randomized controlled trial**

In both groups, intraoperative maintenance rate of crystalloid fluids is  $3 \text{ ml}\cdot\text{kg}^{-1}\cdot\text{hr}^{-1}$ . ProAQT-derived hemodynamic data are acquired at three time periods: before surgical incision, during OLV and at the end of surgery. Subjects randomized to the GDT group will be managed according to the ERAS algorithm utilizing ProAQT variables (mean arterial pressure, stroke volume variation and cardiac index) If stroke volume variation is  $\geq 10\%$ , a bolus of 150 ml of crystalloid fluid will be given until the stroke volume variation is  $< 10\%$ . If mean arterial pressure is  $< 70 \text{ mmHg}$  and/or cardiac index  $< 2.5 \text{ l}\cdot\text{min}^{-1}\cdot\text{m}^{-2}$  despite the stroke volume variation of  $< 10\%$  following fluid challenge, single or consecutive boluses of ephedrine 4 mg and/or continuous intravenous infusion of norepinephrine  $2\text{--}10 \text{ }\mu\text{g}\cdot\text{min}^{-1}$  will be administered. (Figure 1)

[figure not shown]

Figure 1: Goal-directed hemodynamic algorithm to guide intraoperative fluid therapy and the use of vasopressor and inotropic therapy in the goal-directed therapy group

Subjects allocated to the control group are hemodynamically managed as follows. Isolated hypotension (defined as 20% decrease in mean arterial pressure below baseline or < 60 mmHg) is treated by a continuous intravenous infusion of norepinephrine 2–10  $\mu\text{g}\cdot\text{min}^{-1}$ . If hypotension persists, repeat boluses of ephedrine 4 mg will be administered until mean arterial pressure is > 60 mmHg. If hypotension is accompanied by signs of hypovolemia (defined as urine output < 0.5  $\text{ml}\cdot\text{kg}^{-1}\cdot\text{hr}^{-1}$  and/or an increase in heart rate > 20% above baseline), crystalloid fluid will be administered until urine output and/or heart rate are normalized. Colloids are administered only when hypotension develops during acute hemorrhage. If hypotension persists despite volume challenges, norepinephrine will be administered. In both groups, fluid and inotrope or

vasopressor responsiveness and hemodynamic variables will be evaluated each 15 min, and more frequently in case of hemodynamic instability. ProAQT variables will be recorded every 15 min.

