The primary outcome is in-hospital postoperative pulmonary complication, including atelectasis, pleural effusion, pneumonia, empyema, pulmonary embolism, re-operation, and respiratory failure. The diagnosis of atelectasis and pleural effusion will be made based on routinely performed chest radiographs on postoperative days 1 and 3. Pneumonia will be diagnosed if a patient presents with fever, leukocytosis and new infiltrates on chest radiography. Pleural empyema and pulmonary embolism will be confirmed by spiral computed tomography scan. Respiratory failure is defined as described. Secondary outcomes include relative change of PaO2/FiO2, PaO2/FiO2 values after induction of anesthesia and at the end of surgery, acute kidney injury (defined by Acute Kidney Injury Network Criteria), cardiac complications (myocardial infarction diagnosed by electrocardiogram and troponin T serum concentration; newly developed atrial fibrillation), clinically relevant hypotensive episodes (decrease in mean arterial pressure > 20% for more than 15 min requiring vasopressors), newly developed stroke, and length of hospital stay. All outcomes will be determined again 30 days after surgery and documented by research staff blinded to group allocation.

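### Three exclusion criteria can be known only after allocation; applying them contradicts the plan's intention-to-treat statement, and nothing in the plan resolves this

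*Combined protocol and SAP*

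**What the plan says.** Section 3 (Criteria of Eligibility) gives a single list of exclusion criteria. Most are baseline facts such as age, pregnancy or a pacemaker. The same list contains "intraoperative blood loss > 1 L, intraoperative blood transfusion, planned or unanticipated transfer to intensive care unit for postoperative mechanical ventilation". Nothing limits blood loss or transfusion to what is expected before surgery.

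Section 4 (Study Design) has the envelope opened "on the day of surgery immediately before induction of anesthesia". It then states that "we will follow the principle of intention-to-treat in our analyses of the trial results", with no exception and no modified population.

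Section 5 describes two comparisons in the same patients.

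- **M-Entropy:** anaesthetic titration differs by arm. "Primary outcome is time to spontaneous eye opening". The text takes it that "all subjects will be extubated at the operating room and then transferred to the postanesthetic care unit".
- **ProAQT:** fluid and vasopressor rules differ by arm. In the goal-directed arm, when stroke volume variation reaches the threshold, "a bolus of 150 ml of crystalloid fluid will be given until the stroke volume variation is" back under it. Control patients follow a rule based on blood pressure, urine output and heart rate, which includes "Colloids are administered only when hypotension develops during acute hemorrhage". The outcome is defined as follows: "The primary outcome is in-hospital postoperative pulmonary complication, including atelectasis, pleural effusion, pneumonia, empyema, pulmonary embolism, re-operation, and respiratory failure". All outcomes are to be assessed again at 30 days.

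The Statistical Analysis section names tests and regression models. It defines no analysis set and no rule for patients who meet an exclusion criterion after allocation.

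**The concern.** An exclusion criterion that can be met only after allocation is in effect a rule for removing randomised patients. Leaving out patients found to be ineligible can be defended under intention-to-treat when the ineligibility rests on facts fixed before randomisation. These three items do not.

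The excluding events occur while the allocated strategies are being delivered, or soon after. The number or the type of patients removed may therefore depend on the arm, and the comparison would no longer be between the groups that randomisation formed. The anaesthetist delivering the haemodynamic algorithm necessarily knows the arm, and the staff blinding described in Section 5 concerns the postoperative period. Decisions that trigger an exclusion may thus be taken by someone who knows the allocation.

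The events also lie close to the primary outcomes. Unanticipated ventilation may overlap with respiratory failure, a component of the ProAQT composite. Patients who leave theatre sedated or ventilated may have the longest eye-opening times, or none recorded. Because the design is factorial, a patient removed is lost to both comparisons.

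**Working it through.** **Step 1. When each criterion becomes known, against allocation just before induction (Section 4)**

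| Item in Section 3 | Earliest time it can be known | Relative to allocation |
|---|---|---|
| Intraoperative blood loss > 1 L | During surgery | After |
| Intraoperative transfusion | During surgery | After |
| Unanticipated ICU transfer for ventilation | During or after surgery | After |
| Planned ICU transfer for ventilation | Before surgery | Before; not at issue |

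**Step 2. Can the list be read as preoperative expectation only?** No word in Section 3 supports that for blood loss or transfusion. For ICU transfer the word *unanticipated* rules it out, so at least one criterion must operate after allocation.

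**Step 3. Does another part of the plan settle it?** The Statistical Analysis section has no analysis set, no modified intention-to-treat population and no rule for exclusions after allocation. The control-arm haemorrhage rule shows bleeding patients being managed within the trial, and the 30-day reassessment names no exception; neither says who is analysed. The statement on extubation in theatre gives no rule for a patient who stays ventilated. Two analysts could build different analysis sets from the same text.

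**Step 4. Illustration of possible size.** The plan gives no event rates, effect size or sample size, so there is no figure of its own to reproduce, and every input here is assumed. Let p be the true composite risk in an arm, x the proportion excluded after allocation, and r the event risk among those excluded. Then

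analysed risk = (p − x·r) / (1 − x).

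For example, with p = 0.20, x = 0.05 and r = 0.5 in control: (0.20 − 0.025)/0.95 = 18.42%. With p = 0.14, x = 0.02 and r = 0.5 in the goal-directed (GDT) arm: (0.14 − 0.01)/0.98 = 13.27%. The apparent difference is 5.16 points against a true 6.0.

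| True risk, control / GDT | Excluded, control / GDT | Event risk among excluded, control / GDT | Analysed risk, control / GDT | Difference (points) |
|---|---|---|---|---|
| 20% / 14% | 5% / 2% | 50% / 50% | 18.42% / 13.27% | 5.16 |
| 20% / 14% | 2% / 5% | 50% / 50% | 19.39% / 12.11% | 7.28 |
| 20% / 14% | 5% / 2% | 100% / 100% (extreme) | 15.79% / 12.24% | 3.54 |
| 20% / 14% | 2% / 5% | 100% / 100% (extreme) | 18.37% / 9.47% | 8.89 |
| 20% / 14% | 5% / 5% | 60% / 40% | 17.89% / 12.63% | 5.26 |
| 20% / 14% | 5% / 5% | 40% / 60% | 18.95% / 11.58% | 7.37 |
| 20% / 14% | 2% / 2% | 50% / 50% | 19.39% / 13.27% | 6.12 |
| 20% / 20% | 5% / 5% | 60% / 40% | 17.89% / 18.95% | −1.05 |
| 20% / 20% | 5% / 5% | 100% / 50% | 15.79% / 18.42% | −2.63 |

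Two things follow. The distortion can go either way. Equal numbers excluded do not by themselves make the comparison safe: with no true effect and 5% removed from each arm, a spurious difference of 1.05 to 2.63 points appears when the removed patients differ in risk between arms. Equal exclusion is nearly harmless on this scale only when the excluded patients carry similar risk in both arms (the 2% / 2% row).

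**The case against.** The strongest reply is that the contradiction is conditional. Section 3 governs eligibility and Section 4 governs analysis, and neither says outright that a randomised patient who bleeds is deleted. That is fair: what is shown is an unresolved conflict and an undefined analysis set, not a declared plan to drop patients. But a listed exclusion criterion is naturally read as a rule to be applied, and one of these can be applied only after allocation.

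Several further points stand in part.

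- The colloid rule can apply to patients who meet no exclusion, and the 30-day statement may mean only patients still in the study. Neither is more than weak support.
- The statement that all subjects are extubated in theatre is consistent with Section 3 being applied as exclusions, so it may hint at the intended population. It does not reconcile that population with intention-to-treat.
- The documents give no route from anaesthetic titration to blood loss or transfusion. Dependence on the arm is more plausible for the haemodynamic comparison, and for ventilation.
- Overlap with respiratory failure cannot be verified, because that component is defined by citation and the ICU criterion gives no reason or timing for transfer.
- The scenarios rest wholly on assumed rates and cover only the ProAQT outcome.
- A declared modified population with exclusions reported by arm would also remove the textual conflict. It would not remove the risk of bias.

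**Conclusion.** The concern holds. Three of the listed exclusions can be met only after allocation, the intention-to-treat statement admits no exception, and no section says which governs. The population for both primary outcomes is therefore undetermined, and this cannot be settled neutrally once results have been seen. It must be fixed.

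That conclusion rests on the text, not on the scenarios. The size and direction of any bias are unknown. Under the assumed risks of 20% and 14%, the apparent difference ranged from 3.5 to 8.9 points around a true 6.0, with the ends of that range requiring every excluded patient to have an event. The actual effect could be small if few patients meet these criteria or if those who do are alike in both arms.

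**What to change.** Reconcile Sections 3 and 4, and add an analysis-set definition to the Statistical Analysis section.

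1. Keep as exclusions only criteria that can be established before the envelope is opened, including planned ICU transfer for ventilation. Remove the three items that arise after allocation.
2. Follow every randomised patient and analyse each in the allocated arm for both primary outcomes.
3. Count unanticipated ventilation in the ProAQT composite whenever it meets the respiratory-failure definition the plan already cites.
4. For eye opening, use the observed time wherever there is one. Prespecify one rule for patients who leave theatre still sedated or ventilated, matched to the chosen test. Options are to keep them as not yet awake up to a common truncation time for a log-rank test, or to assign the worst rank for a Wilcoxon test. This choice is part of defining what the comparison estimates, so its rationale should be stated.
5. Report the three events by arm, and use the set that excludes these patients only as a labelled sensitivity analysis.

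The cost is protocol and SAP wording, plus outcome follow-up for patients who would otherwise have been dropped; the documents do not let their number be estimated. Emergence times may become more variable.
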